6.1. Study Visits

6.1.1. Screening Period and Enrollment

Informed consent must be obtained before any study-related procedures are conducted. All study-specific screening procedures must be completed within 28 days (refer to Table 8 for screening procedures). At the baseline visit (Day -3), all pretreatment screening procedures/assessments must be completed and laboratory results confirmed prior to enrollment and the first injection of GM-CSF.

If a patient does not meet inclusion/exclusion criteria within 28 days of signing the ICF, the patient will be considered a screen failure and may be allowed to re-screen with a newly signed ICF up to 2 times.

6.1.2. Open-Label Treatment Period

Refer to [Section 5](#) (Study Treatments) and Table 8 (Schedule of Assessments) for further details.

6.1.3. End of Treatment/Early Termination Visit

Patients who complete the protocol-specified study injections or scheduled study visit evaluations, or who discontinue because of any reason other than recurrent/refractory/relapsed disease will return to the site 30 days after their last injection for final safety follow-up and completion of the EOT/early termination procedures.

6.1.4. Safety Follow-up Period

Patients who complete the study treatment period or discontinue early (if they have received at least 1 treatment injection) will enter an off-treatment follow-up period to assess progression-free survival and overall survival. A follow-up telephone call for serious adverse events will occur 90 days after the last dose of pembrolizumab or 30 days following cessation of study treatment if the patient begins new anticancer therapy, whichever is

earlier. If the patient initiates new anticancer therapy, this must be reported by the investigator. Patients will be followed in accordance with standard guidelines, which suggest regular assessments every 3 months until study closure, defined as up to 2 years and 6 weeks, i.e., 111 weeks, after the first galipepimut-S administration given to the last patient enrolled into the study (which corresponds to up to 2 years after the first injection of pembrolizumab).

6.1.5. Relapse Visit

In addition to the SOA above, one additional series of assessments will be performed at the time of tumor (or leukemia) relapse. Indeed, to assess PFS, it is important to document disease relapse. At the time of the “relapse visit”, the following assessments will be performed:

- Collect and update concomitant medication information
- Collect and update AEs
- Obtain ECOG performance score
- Obtain vital signs and document weight
- Collect blood samples for the central laboratory
 - Hematology (CBC with differential and platelet count)
 - Serum chemistry
 - Immune/exploratory correlates
- Evaluate clinical endpoints

For AML patients in specific, PB differentials from CBCs collected during every visit will be used to determine initially if the patient has relapsed, as defined by loss of CR status (if previously achieved) or further progression beyond initially achieved PR. For abnormal CBCs, a manual differential is required. If the differential is suggestive of abnormal or

immature cells and a possible relapse, a BM aspiration must be performed as part of a scheduled relapse visit to confirm the diagnosis of recurrent/relapse/refractory AML. A BM biopsy must be performed if an adequate aspiration is not attainable. In patients with AML who achieve CR status while on investigational therapy (galinpepimut-S plus pemrolizumab – administered on top of their continuing HMA regimen), relapse (post-CR) will be defined as a reappearance of leukemic blasts in the PB or >5% blasts in the BM not attributable to any other cause (e.g., BM regeneration after chemotherapy [[Cheson et al, 2003](#)]). If relapse is confirmed, the patient should be discontinued from the on-treatment portion of the study due to recurrent/refractory/relapsed AML and will need to return to the site 0 to 30 days after their last treatment injection for final safety follow-up and completion of the EOT/early termination visit procedures. The BM aspiration performed as part of the scheduled relapse visit will serve as BM aspiration procedure required at the EOT/early termination visit.

Once EOT/early termination visit procedures have been completed, the physician can choose to treat the documented recurrent/refractory/relapsed disease with any subsequent therapy they choose. The patient will be moved to the off- treatment follow-up period and will be followed only for AEs and OS.

6.1.6. Unscheduled Visits

As appropriate, assessments at any unscheduled visit should follow the assessments at the closest weekly/monthly/quarterly visit.

6.2. Efficacy Assessments

Signal response for each a priori statistically defined clinical outcome (ORR per RECIST 1.1) for all patients enrolled in the solid tumor arms of the study or other appropriate instruments scales, such as attainment of morphologic CR in patients enrolled in the AML arm. In addition to RECIST 1.1, all scans will be read according to iRECIST immune response consensus guideline ([Seymour et al, 2017](#)) to ensure that patients are not discontinued from therapy due to the phenomenon of tumor “pseudoprogression”, and clinical decisions will be based on iRECIST ([Hodi et al, 2016](#)). ORR per iRECIST will be an exploratory endpoint of this study.

6.3. Exploratory Assessments

Assessment of tumor response in solid tumor patients by iRECIST, as well as estimation of the rate of achievement of MRD negativity in AML patients are exploratory endpoints in this study.

All patients will be followed and assessed for PFS and OS, as per the schedule of assessments and using the ITT principle.

As an exploratory evaluation, this study will assess the effect of the study treatment on readouts of immunologic tests in PB samples (see below), as well as presence and density of immune cell infiltrates within the tumor stroma (or BM in AML patients) using at least one post-therapy tumor biopsy (and comparing the findings with those at baseline, i.e., prior to initiation of treatment).

In more detail:

In peripheral blood:

The following parameters will be tested:

- *Galinpepimut-S* -relevant immune response-relevant:
- *WT1* peptide--specific CD8 and CD4 cell frequencies:
 - Cell frequencies (absolute cell abundance/numbers/microliter of blood) of host CD8 and CD4 cells that react with increased production of intracellular interferon- γ as detected by intracellular cytokine staining (ICS) after ex vivo re-stimulation (Pinella-Ibarz et al, 2006; Gomez-Nunez et al, 2006; Maslak et al, 2010) with the following peptides:
 - WT1A1 (heteroclitic)
 - WT1A (cognate native of the one above)

- 122A1 (heteroclitic)
- 122A (cognate native of the one above)
- 331 (native)
- 427 (native)
- *Complete lymphocyte population panel (non-antigen-specific)*

Cell frequencies (absolute cell abundance/numbers/microliter of blood) - for each patient at each timepoint of collection, as follows:

- Naïve T cells: CD45RA+CD45RO-CCR7+CD62L+CD57-
- Central memory T cells: CD45RA-CD45RO+CCR7+CD62L+CD57-
- Effector memory T cells: CD45RA-CD45RO+CCR7-CD62L-CD57+
- Total effector cells: CD45RA+CD45RO-CCR7-CD62L-CD57+
- Tregs: FoxP3+, CD25+, PD1, ICOS
- Myeloid-derived suppressor cells (MDSC's):
- PMN-MDSC's: CD14-CD11b+CD15+(or CD66b+) and
- M-MDSC's: CD11b+CD14+HLA-DR^{low}/-CD15-
- Thus, the following antibody “gates” would have to be utilized in methodology selected (see Laboratory Manual): CD3, CD4, CD8, CD45RA or CD45RO, CD57, and CCR7 or CD62L or CD27, FoxP3, CD25, PD1, ICOS, CD14, CD11b, CD15; HLA-DR
- **In tumoral biopsy samples (TBx):**

- *Galinpepimut-S -relevant*
- The following parameters will be tested:
 - Intratumoral CD8 and CD4 (cells within tumor stroma versus surrounding the tumor proper) ([Arlen and Arlen, 2013](#))
 - MDSC, T-regulatory cells (Treg), and tumor-associated macrophages (TAMs)

General (non-antigen-specific) immunodynamics

- PDL1 expression and Interferon- γ tissue inflammatory gene expression ‘signature’ assessment

Genetic (DNA) analyses

- The application of new technologies, such as next generation sequencing, has provided scientists the opportunity to identify tumor-specific DNA changes (i.e., mutations, methylation status, microsatellite instability, etc.). Key molecular changes of interest to immune-oncology drug development include (for example) the mutational burden of tumors and the clonality of T cells in the tumor microenvironment. Increased mutational burden (sometimes referred to as a “hyper-mutated” state) may generate neo-antigen presentation in the tumor microenvironment. To conduct this type of research, it is important to identify tumor-specific mutations that occur across all genes in the tumor genome. Thus, genome wide approaches will be used for this effort. Note that in order to understand tumor-specific mutations; it is necessary to compare the tumor genome with the germline genome.
- Specifically for CRC patients:
 - MSI will be evaluated in all CRC patients enrolled in this study, as this is an important biomarker for this type of cancer.

6.4. Safety Assessments

Patients will be monitored for AEs and will undergo safety assessments including vital signs and weight, ECOG performance status, and clinical laboratory testing, which will include CBC with differential and platelet count, serum chemistry assessment, and urine dipstick test.

6.4.1. Adverse Events

The investigator is responsible for reporting all AEs that are observed or reported during the study, regardless of their relationship to study treatment or their clinical significance. If AEs occur, the first concern will be the safety of the study patients.

Any abnormal laboratory test results (hematology, clinical chemistry, or urine dipstick) or other abnormal finding or safety assessments (e.g., vital sign measurements), including those that worsen from baseline, felt to be clinically significant in the medical and scientific judgment of the investigator will be graded by CTCAE v5.0 criteria and are to be recorded as AEs or SAEs.

Adverse event monitoring will occur from the time of signing the ICF to 30 days after the last injection of study treatment.

6.4.1.1. Definitions of Adverse Events

An AE is defined as any untoward medical occurrence in a patient enrolled into this study and does not necessarily have to have a causal relationship (association) with this treatment. An AE can therefore be any unfavorable or untoward sign, symptom, disease, syndrome, intercurrent illness, or abnormal laboratory finding that emerges or worsens relative to the patient's pretreatment baseline, whether or not it is considered to be related to the investigational product.

A TEAE is defined as any event not present before exposure to study treatment or any event already present that worsens in either intensity or frequency after exposure to study treatment.

An SAE is any AE at any dose that:

- Results in death
- Is life-threatening
- Requires inpatient hospitalization or prolongation of existing hospitalization
- Results in persistent or significant disability/incapacity
- Is a congenital anomaly/birth defect
- Constitutes an important medical event (i.e., the AE did not meet any of the above serious criteria but based on appropriate medical judgment, may have jeopardized the patient or required medical or surgical intervention to prevent one of the serious outcomes listed in these criteria)

6.4.1.2. Eliciting and Documenting Adverse Events

Adverse events will be assessed from the time the patient signs the ICF until 30 days after the last study treatment injection. Adverse events collected before injection of study treatment will be reported as pretreatment AEs and those collected after the first injection of GM-CSF and throughout the study will be reported as TEAEs. Serious AEs that occur more than 30 days after the last dose of study treatment need not be reported unless the investigator considers them related to study treatment. Any medical condition that is present at the time that the patient is screened but does not deteriorate should not be reported as an AE. However, if it deteriorates at any time during the study, it should be recorded as an AE.

At every study visit, patients will be asked a standard nonleading question to elicit any medically related changes in their well-being. They will be asked if they have been hospitalized, had any accidents, used any new medications, or changed concomitant medication regimens (both prescription and over-the-counter medications) or therapies. Patients will also be instructed to contact the investigator at any time after beginning study treatment if any signs or symptoms develop.

In addition to patient observations, AEs identified from any study data (e.g., laboratory values), or identified from review of other documents that are relevant to patient safety will be documented on the AE page in the eCRF.

All AEs must be documented on the AE pages of the eCRF and in the patient's medical record. The following attributes must be assigned: (1) description; (2) dates of onset and resolution; (3) severity (per CTCAE v5.0); (4) assessment of relatedness to the study medication (unrelated, possible, probable, definite); (5) "serious" criteria if applicable (see [Section 6.4.1.3](#) on how to report SAEs); (6) action taken; and (7) outcome (recovered/resolved, not recovered/resolved, recovered/resolved with sequelae, ongoing, or death). The investigator will actively solicit this information and assess the AEs in terms of severity and relationship to study treatment. The investigator will treat the patient as medically required until the AE either resolves or becomes medically stable. Treatment for AEs may extend beyond the duration of the study. The investigator will record treatment and medications required for treatment on the appropriate eCRF(s). In the event that a patient is withdrawn from the study because of an AE or SAE, it must be recorded on the Termination eCRF as the reason for discontinuation. The Medical Dictionary for Regulatory Activities (MedDRA) will be used to code all AEs.

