5.3.6.3. Dose Modification and Toxicity Management Guidelines for Pembrolizumab

5.3.6.3.1. Dose Modification and Toxicity Management for Immune-related AEs (irAEs) Associated with Pembrolizumab

AEs associated with pembrolizumab exposure may represent an immunologic etiology. These immune-related AEs (irAEs) may occur shortly after the first dose or several months after the last dose of pembrolizumab treatment and may affect more than one body system simultaneously. Therefore, early recognition and initiation of treatment is critical to reduce complications. Based on existing clinical trial data, most irAEs were reversible and could be managed with interruptions of pembrolizumab, administration of corticosteroids and/or other supportive care. For suspected irAEs, ensure adequate evaluation to confirm etiology or exclude other causes. Additional procedures or tests such as bronchoscopy, endoscopy, skin biopsy may be included as part of the evaluation. Based on the severity of irAEs, withhold or permanently discontinue pembrolizumab and administer corticosteroids. Dose modification and toxicity management guidelines for irAEs associated with pembrolizumab are provided in [Table 5](#).

Table 5 Dose Modification and Toxicity Management Guidelines for Immune-related AEs Associated with Pembrolizumab

General instructions:
 
 1. Corticosteroid taper should be initiated upon AE improving to Grade 1 or less and continue to taper over at least 4 weeks. 2. For situations where pembrolizumab has been withheld, pembrolizumab can be resumed after AE has been reduced to Grade 1 or 0 and corticosteroid has been tapered. Pembrolizumab should be permanently discontinued if AE does not resolve within 12 weeks of last dose or corticosteroids cannot be reduced to ≤ 10 mg prednisone or equivalent per day within 12 weeks. 3. For severe and life-threatening irAEs, IV corticosteroid should be initiated first followed by oral steroid. Other immunosuppressive treatment should be initiated if irAEs cannot be controlled by corticosteroids. 				
Immune-related AEs	Toxicity grade or conditions (CTCAEv5.0)	Action taken to pembrolizumab	irAE management with corticosteroid and/or other therapies	Monitor and follow-up

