- ^t. Immediately after the patient receives the GM-CSF injection, patients are to receive galinepimut-S injected SC in the same anatomical location as the GM-CSF injection. The injection site should be on the arm, leg, or torso of the patient, and should be positioned at least 5 cm away from the previous site of study treatment injection.
- ^u. Adverse event reporting begins from the time of signing the ICF to 30 days after the last injection of any study treatment (GPS/placebo or pembrolizumab). Adverse events collected before the first injection of GM-CSF will be reported as “pre-WT1 AEs”. All AEs will be graded by

CTCAE, Version 5.0. A follow-up phone call for serious adverse events will occur 90 days after the last dose of pembrolizumab or 30 days following cessation of study treatment if the patient begins new anticancer therapy, whichever is earlier. If the patient initiates new anticancer therapy, this must be reported by the investigator.

- v. Patients who complete the study, or who discontinue because of any reason other than recurrent/refractory/relapsed disease will return to the site 30 days after their last injection for final safety follow-up and completion of EOT/ET visit.
- w. Only to occur at Week 9.
- x. Only to occur at Week 36.
- y. Only to occur at Week 54.
- z. Only to occur at Weeks 72 and 84.
- aa. Only to occur at Weeks 27 and 36.
- bb. Only to occur at Weeks 45, 54, and 63.

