6.4.1.7. Follow-Up of Patients Reporting Adverse Events

All AEs must be reported in detail on the appropriate page in the eCRF and followed to satisfactory resolution, until the investigator deems the event to be chronic or not clinically significant, or until the patient is considered to be stable.

For SAEs, the investigator will follow the patient until the SAE resolves, returns to baseline condition or stabilization, or is determined to be permanent, whichever occurs first. Serious AEs that are ongoing at the time of clinical database closure will be recorded as ongoing on the eCRF page. A follow-up phone call for SAEs will occur 90 days after the last dose of pembrolizumab or 30 days following cessation of study treatment if the patient begins new anticancer therapy, whichever is earlier. If the patient initiates new anticancer therapy, this must be reported by the investigator.

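### Section 6.4.1.2 excuses unrelated SAEs after day 30, contradicting the 90-day SAE call and the protocol's other SAE reporting rules

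*Combined protocol and SAP*

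**What the plan says.** Section 6.4.1.2 sets the general window: "Adverse events will be assessed from the time the patient signs the ICF until 30 days after the last study treatment injection". For later serious events it adds: "Serious AEs that occur more than 30 days after the last dose of study treatment need not be reported". The one exception it makes is for an event that the investigator judges to be related. Section 6.4.1 and Table 8 footnote u also end adverse event collection at day 30; the footnote reads "Adverse event reporting begins from the time of signing the ICF to 30 days after the last injection of any study treatment".

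Section 6.4.1.7 then states: "A follow-up phone call for SAEs will occur 90 days after the last dose of pembrolizumab". A shorter limit is set for patients who move on to other treatment, whose call falls "30 days following cessation of study treatment if the patient begins new anticancer therapy, whichever is earlier". The same call appears in the Synopsis (Procedures and Safety Assessments), Section 6.1.4 and Table 8 footnotes c and u. None of these places confines it to related events.

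Two other sections bear directly on the question. Section 6.4.1.3 requires any adverse event meeting SAE criteria to be reported within 24 hours of site awareness, and all deaths whether or not related; it sets no day-30 limit. Section 6.4.1.5 says the causality assessment does not determine what is reported.

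On late toxicity, Section 5.3.6.3.1 says: "These immune-related AEs (irAEs) may occur shortly after the first dose or several months after the last dose of pembrolizumab treatment". Safety and tolerability are a primary objective (Section 2.1) and a primary endpoint (Section 7.1). Section 7.6.4.1 tabulates SAE incidence but does not say over what window.

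**The concern.** A site that learns at the 90-day call of an SAE it considers unrelated has no single instruction to follow. One section says it need not report the event, another says to report it within 24 hours, and a third says causality is irrelevant to reporting. Because Section 6.4.1.2 permits omission without forbidding reporting, two sites can both comply and still submit different data.

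The stake is the SAE table for a primary outcome. Section 2.1 hypothesises an adverse event profile comparable with pembrolizumab monotherapy, so the SAE count needs a defined window. The events most exposed are those whose cause is easy to mistake: a late immune-related event attributed to disease or, in the AML arm, to the continuing hypomethylating agent. The study is open-label (Section 5.4.4), and Sections 6.5 and 10.1 provide no safety or data monitoring committee to look again at an unrelated call. Section 7.6.4.1 imputes missing relatedness as related, but that safeguard cannot reach an event that was never reported.

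**Working it through.** The plan states no figure on this point, so the check is a comparison of the rules, followed by an illustration under stated assumptions.

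**1. Rules applied to one case.** Take a non-fatal hospitalisation on day 60 after the last pembrolizumab dose, judged unrelated, with no new anticancer therapy, learned of at the 90-day call.

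| Place | What the site should do |
|---|---|
| 6.4.1.2 | Need not report |
| 6.4.1 and Table 8 footnote u (AE window) | Outside the 30-day window |
| 6.4.1.7, 6.1.4, Table 8 footnotes c and u (call) | The call is made to ask about SAEs; no causality limit |
| 6.4.1.3 | Report within 24 hours of awareness |
| 6.4.1.5 | Causality does not decide reporting |

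**2. Which events are exposed.**
- Fatal: reportable regardless of relationship (6.4.1.3). Not exposed.
- Non-fatal, judged related: reportable after day 30 with no time limit (6.4.1.2). Not exposed.
- Non-fatal, judged unrelated, day 31 to the call: conflicting instructions. Exposed.
- Patients who start new anticancer therapy: the call moves to 30 days after cessation, so little or no gap remains before it.

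**3. Calendar span.** For patients without new therapy, the conflict covers 90 − 30 = 60 days. This is the span under conflicting rules, not follow-up that is lost.

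**4. Illustration only.** The documents give neither a late-SAE rate nor a share judged unrelated. Assume that a fraction r of patients has a non-fatal SAE after day 30, that a fraction q of these is judged unrelated, and that every site omits them. Then the expected number of patients with an unreported event is n × r × q, and the chance of at least one is 1 − (1 − rq)^n.

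| n | r | q | Expected unreported | Chance of at least one |
|---|---|---|---|---|
| 90 | 2% | 25% | 90 × 0.02 × 0.25 = 0.45 | 1 − 0.995^90 = 36% |
| 90 | 5% | 50% | 90 × 0.05 × 0.50 = 2.25 | 1 − 0.975^90 = 90% |
| 90 | 10% | 75% | 90 × 0.10 × 0.75 = 6.75 | 1 − 0.925^90 = 99.9% |
| 20 | 2% | 25% | 20 × 0.02 × 0.25 = 0.10 | 1 − 0.995^20 = 10% |
| 20 | 10% | 75% | 20 × 0.10 × 0.75 = 1.50 | 1 − 0.925^20 = 79% |

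The effect on SAE incidence would be smaller where the same patient already has a reported SAE.

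**The case against.** The strongest reply is that the scheme has two tiers: all adverse events to day 30, then a check at day 90 for the late related SAEs that Section 6.4.1.2 still requires. On that reading the call keeps a purpose. A late immune-related event recognised as such is captured, and the protocol's category of possible relationship is a low bar. Other text also leans towards broad collection: Section 3.1 promises long-term safety follow-up, Section 6.1.5 follows relapsed patients for adverse events, and the adverse event row of Table 8 appears to be marked in the off-treatment column.

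Much of this stands. A reader might infer that the 30-day rule makes the call pointless. It does not, because the call can still find related SAEs. A reader might also infer that 60 of the 90 days of follow-up are lost. They are not: the call takes place, and deaths and related SAEs are reported throughout.

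The two-tier reading does not settle the matter, however. No passage restricts the call to related events, and Sections 6.4.1.3 and 6.4.1.5 state the opposite principle. That other passages favour broad collection is what makes Section 6.4.1.2 inconsistent with them.

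**Conclusion.** The inconsistency is real and should be corrected. It is limited to non-fatal SAEs judged unrelated between day 31 and the 90-day call, in patients who have not started new anticancer therapy. These may be collected inconsistently or left out of the primary safety data. The documents supply no rate from which to size the effect; the range of 0.45 to 6.75 of 90 patients rests wholly on assumed inputs and on every site taking the permissive reading.

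Two stronger conclusions are tempting. One is that the safety data are truncated. The text supports only that they may be, because other sections require the same events to be reported. The other is that the SAE rate is biased downward against pembrolizumab monotherapy. Omission can only lower the observed count, but the comparison is with historical data whose SAE window the documents do not give, so the direction of any bias in the comparison is not established. The SAE stopping rules in Sections 5.3.6.1 and 5.3.6.2 count only events at least possibly attributable, so leaving out SAEs judged unrelated does not change those counts.

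**What to change.** Amend Section 6.4.1.2 so that SAEs are recorded regardless of causality up to the call already scheduled: 90 days after the last pembrolizumab dose, or 30 days after cessation if new anticancer therapy starts, whichever is earlier. Keep SAEs judged related reportable after that. Align the SAE wording in Section 6.4.1, Table 8 footnote u and Section 6.4.1.8, whose events of clinical interest include selected SAEs and currently stop at 30 days. The window for non-serious events can stay as it is. Because pembrolizumab starts at Week 6, also say from which date the window runs for a patient who stops before then.

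In Section 7.6.4.1, state which window the SAE tables use. A 30-day SAE tabulation can be shown alongside for comparison with historical data.

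The cost is wording plus a few more SAE forms from a call already planned. Reported SAE incidence may rise somewhat. Neither treatment nor the visit schedule changes.
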